**Exclusion Criteria:**

- 1) Patients with non-Chinese nationalities.
- 2) Duplicated storage (records with same inpatient code).

**9.2.3 Study visits**

Not applicable

**9.2.4 Study discontinuation**

Boehringer Ingelheim reserves the right to discontinue the study at any time for the following reasons:

1. Failure to reach eligible analyzable population/data
2. Violation of Good Pharmacoepidemiology Practice (GPP), the study protocol, or the contract by a study site, investigator or research collaborator, disturbing the appropriate conduct of the study

The investigator /research collaborator will be reimbursed for reasonable expenses incurred in case of study termination defined in a contract filed before the initiation of the study (except in case of the third reason).

**9.3 VARIABLES**

The following variables will be collected in this study.

- 1) Demographic characteristics of the patients: age, gender, type of health insurance, etc.
- 2) Status of the patient's disease diagnosis: outpatient diagnosis, discharge diagnosis.
- 3) Information on the patient's laboratory tests, glycated haemoglobin, blood glucose, blood creatinine, estimated glomerular filtration rate, urine microalbumin, lipids, etc.
- 4) Patient medication and treatment: including CVD-related treatment (antiplatelet agents, statins, vasodilators), diabetes-related treatment (insulin, oral hypoglycaemic agents),

hypertension-related treatment (e.g. calcium antagonists, angiotensin-converting enzyme antagonists, angiotensin receptor antagonists, beta-receptor antagonists, etc.), hyperlipidaemia-related treatment (e.g. lipid-lowering drugs), CKD-related treatment (e.g., dialysis, angiotensin-converting enzyme antagonists, angiotensin receptor antagonists, kidney transplantation), etc.

- 5) Number of days the patient was hospitalized
- 6) Patient's medical costs, including all costs during hospitalization (hospitalization, drugs, surgery, etc.)

Table 1. variables collected from database

Table Name	Variables
Basic information	medical organization
	unique ID of patients
	birthday
	sex
	ethic
	type of insurance
Laboratory	unique ID of patients
	report number
	test date
	test time
	item test name
	item test result
	item test unit
	item test sample
item test range	
Diagnosis	unique ID of patients
	diagnosis
	admission status
	discharge status
	diagnosis date
	department
Advice	unique ID of patients
	advice item name
	dose per time

	total dose
	unit of dosage
	frequency
	advice start date
	advice stop date
Front sheet	unique ID of patients
	admission department
	admission date
	discharge department
	discharge date
	length of hospital stay
	discharge way
Fee information	unique ID of patients
	fee item name
	unit price
	quantity
	total price
	charge date

**9.3.1 Exposures**

Not applicable.

We defined four groups (group A-D) according to the diagnosis and laboratory measurements. The group A and group B included all diabetic patients with/without established CV disease, CKD, or at high CV risk, respectively. The group C included all non-diabetic patients with established cardiovascular disease, chronic kidney disease, or at high cardiovascular risk. The group D included non-diabetic patients without established cardiovascular disease, chronic kidney disease, and not at high cardiovascular risk. For group D, we will randomly sample study populations to acquire a 1:1 sample of non-diabetic patients without disease by matching on age and gender with group A.

**9.3.2 Outcomes**

Our primary outcomes will be the proportion of diabetic/non-diabetic patients with disease/risk. Secondary outcomes include demographic characteristics (e.g. age, gender, insurance payment) and clinical characteristics (e.g. HbA1c, random blood glucose, serum creatine) of patients. Further outcomes include economic burden of disease of diabetic/non-diabetic patients with or without disease/risk (e.g. length of stay, hospital cost).

**9.3.2.1 Primary outcomes**

1. The proportion of diabetic/non-diabetic patients with established cardiovascular disease, or chronic kidney disease, or at high cardiovascular risk.
2. The proportion of diabetic patients with established cardiovascular disease, or chronic kidney disease, or at high cardiovascular risk among all diabetic patients.
3. The proportion of non-diabetic patients with established cardiovascular disease, or chronic kidney disease, or at high cardiovascular risk among all non-diabetic patients.

**9.3.2.2 Secondary outcomes**

1. The demographic characteristics of the latest visit for all patients, as well as the trends for inpatients over time (2015, 2017, and 2019 respectively):
  - 1) Age at admission
  - 2) Gender
  - 3) Insurance payment
2. The clinical characteristics of the studied population of the latest visit for all patients, as well as the trends for inpatients over time (2015, 2017, and 2019 respectively):
  - 1) Discharge department
  - 2) Death
  - 3) Laboratory test results:
    - a) HbA1c
    - b) random blood glucose
    - c) serum creatine

**9.3.3 Covariates**

No Applicable.

## **9.4 DATA SOURCES**

Tianjin regional database cover individual-level health information. There were 40 tertiary hospitals, 32 secondary hospitals and 276 community hospitals Tianjin. It has approximately 200,000 discharges annually. Through integrating EMR systems of hospitals by patient unique identify code, the database contains comprehensive information regarding clinical care, such as patients' basic information, medical advice, diagnosis, laboratory examination, medical records and medical costs. It could be a valuable big data resource for clinical studies. Till 2020, data from 40 tertiary hospitals has been collected, and there were approximately 600,000 patients diagnosed with diabetes in these 40 tertiary hospitals from 01/01/2015 to 31/12/2019. Of these, 100,000 patients were with comprehensive information through integrating EMR systems.

## **9.5 STUDY SIZE**

This study is a database research project using an established regional database in Tianjin. From 01/01/2015 to 31/12/2019, about 600,000 patients diagnosed as diabetes in Tianjin. Of which, 100,000 patients contained comprehensive information about patients' basic information, medical advice, diagnosis, laboratory examination, medical records and medical costs.

## **9.6 DATA MANAGEMENT**

The data management plan is summarized below. Full details of the data management plan are documented in a separate NIS-Data Management and Review Plan (NIS-DMRP). This study will use de-identified data which contains a significant level of protection against the release of personal information to outside entities. The investigator or qualified designee is responsible for recording and verifying the accuracy of subject data.

## **9.7 DATA ANALYSIS**

The statistical analysis plan for the study is summarized below. Full details of the statistical analysis will be documented in the SEAP, which will be finalized before the end of data collection.

### **9.7.1 Main analysis**

Before analyses start, 200 randomly selected medical chart will be fully reviewed by well-trained experts to validate the accuracy and sensibility of code used to identify patients with cardiovascular disease or at high cardiovascular risk, chronic kidney disease and type 2 diabetes. This QC procedure for database study would be performed by [REDACTED].

The analyses will mainly describe the patient demographic characteristics, comorbidities, treatment pattern and economic burden based on 40 hospitals EMRs of Tianjin regional database. Descriptive data will be provided. The statistical methods and analyses will be described in detail in a Statistical and Epidemiological Analysis Plan (SEAP) prior to the commencement of any analyses.

Characteristics presented as continuous data will be summarized through means, standard deviations, medians, minimum and maximum values, whereas, categorical data will be summarized as counts and proportions.

All tests will be two-sided unless otherwise specified

### **9.7.3 Safety Analysis**

*Not applicable*

### **9.8 QUALITY CONTROL**

The quality control and review are summarized below. Greater details are documented in the NIS-DMRP.

The investigator is responsible for implementing and maintaining a quality management system with written development procedures and functional area standard operating procedures (SOPs) to ensure that studies are conducted and data are generated, documented, and reported in compliance with the protocol, accepted standards of Good Pharmacoepidemiology Practice, and all laws, rules and regulations relating to the conduct of the study.

### **9.9 LIMITATIONS OF THE RESEARCH METHODS**

There is no unique ICD code for cardiovascular disease, CKD or at high cardiovascular risk. Each of those diseases has more than one ICD code in the medical charts. The subjects came from different hospitals; the understanding of ICD code may be different according to different hospitals.

The study is limited in representativeness and generalizability. Of 600,000 patients, only 100,000 patients contained comprehensive information about patients' basic information, medical advice, diagnosis, laboratory examination, medical records and medical costs.

### **9.10 OTHER ASPECTS**

#### **9.10.1 Data quality assurance**

A quality assurance audit/inspection of this study may be conducted by the sponsor or sponsor's designees or by regulatory authorities. The quality assurance auditor will have access to all results of the study, the investigator's study-related files and correspondence, and the informed consent documentation of this study.

#### **9.10.2 Study records**

None

### **10. PROTECTION OF HUMAN SUBJECTS**

The section is not applicable since this is a non-interventional study based on existing database.

The procedures set out in this study protocol are designed to ensure that the sponsor and investigator abide by the principles of the GPP guidelines. The study also will be carried out in keeping with local legal requirements and BI Standard Operating Procedures (SOPs).

#### **10.1 STUDY APPROVAL, PATIENT INFORMATION, AND INFORMED CONSENT**

This NIS will be initiated only after all required legal documentation has been reviewed and approved by the respective Institutional Review Board (IRB)/Independent Ethics Committee (IEC) and Competent Authority (CA) according to national and international regulations. The same applies for the implementation of changes introduced by amendments.

#### **10.2 STATEMENT OF CONFIDENTIALITY**

The study will use MD-5 to de-identify personal information in the data including names, ID-numbers, visit numbers, home addresses, etc. against the release of personal information to outside entities. Informed patient consent could be waived. BI will not access data at individual level, but only aggregate results will be obtained.

#### **11. MANAGEMENT AND REPORTING OF ADVERSE EVENTS/ADVERSE REACTIONS**

The current study is an analysis of the existing data collected from the Tianjin regional database. Boehringer Ingelheim or third party acting on behalf of BI will not have access to individual patient data during the study. Data will be provided to BI in aggregated manner. Thus, collection and reporting of adverse events (AEs)/adverse drug reactions (ADRs) is not applicable.

#### **12. PLANS FOR DISSEMINATING AND COMMUNICATING STUDY RESULTS**

The rights of the investigator and of the sponsor with regard to publication of the results of this study are described in the investigator contract. As a general rule, no study results should be published prior to finalization of the NIS Report.

The final publication will be written after the final NIS report is completed.

BI intends to use data from this study to prepare peer-reviewed publications and other scientific communications, study protocol and final study report planned for American Diabetes Association Scientific Sessions 2022.

The final report plan to be published in Diabetes Research and Clinical Practice.

Results of this NIS will be disclosed on [clinicaltrials.gov](http://clinicaltrials.gov) and [encepp.eu](http://encepp.eu) once available.

## ANNEX 1. LIST OF STAND-ALONE DOCUMENTS

Number	Document Reference Number	Date	Title
1	Not applicable	21 May 2021, Version 1.0	Data Management Review Plan (DMRP)
2	Not applicable	13 May 2021, Version 1.0	Statistical and Epidemiological Analysis Plan (SEAP)

## ANNEX 2. ENCEPP CHECKLIST FOR STUDY PROTOCOLS

**Study title:** *Clinical characteristics and disease burden of patients with diabetes mellitus combined with cardiovascular or chronic kidney disease based on regional medical database in Tianjin China*

**EU PAS Register® number:** 38023  
**Study reference number (if applicable):** 1245-0203

Section 1: Milestones	Yes	No	N/A	Section Number
1.1 Does the protocol specify timelines for				
1.1.1 Start of data collection 				6
1.1.2 End of data collection 				6
1.1.3 Progress report(s)				6
1.1.4 Interim report(s)				6
1.1.5 Registration in the EU PAS Register®				6
1.1.6 Final report of study results.				6

Comments:

--

Section 2: Research question	Yes	No	N/A	Section Number
2.1 Does the formulation of the research question and objectives clearly explain:				7& 8& 9

 Date from which information on the first study is first recorded in the study dataset or, in the case of secondary use of data, the date from which data extraction starts.

 Date from which the analytical dataset is completely available.

Section 2: Research question	Yes	No	N/A	Section Number
2.1.1 Why the study is conducted? (e.g. to address an important public health concern, a risk identified in the risk management plan, an emerging safety issue)				7
2.1.2 The objective(s) of the study?				8
2.1.3 The target population? (i.e. population or subgroup to whom the study results are intended to be generalised)				9.2.2
2.1.4 Which hypothesis(-es) is (are) to be tested?				
2.1.5 If applicable, that there is no a priori hypothesis?				

Comments:

Section 3: Study design	Yes	No	N/A	Section Number
3.1 Is the study design described? (e.g. cohort, case-control, cross-sectional, other design)				9.1
3.2 Does the protocol specify whether the study is based on primary, secondary or combined data collection?				9.4
3.3 Does the protocol specify measures of occurrence? (e.g., rate, risk, prevalence)				9.3.2
3.4 Does the protocol specify measure(s) of association? (e.g. risk, odds ratio, excess risk, rate ratio, hazard ratio, risk/rate difference, number needed to harm (NNH))				
3.5 Does the protocol describe the approach for the collection and reporting of adverse events/adverse reactions? (e.g. adverse events that will not be collected in case of primary data collection)				

Comments:

Section 4: Source and study populations	Yes	No	N/A	Section Number
4.1 Is the source population described?				9.2
4.2 Is the planned study population defined in terms of:				
4.2.1 Study time period				9.2
4.2.2 Age and sex				9.2
4.2.3 Country of origin				9.2
4.2.4 Disease/indication				9.2
4.2.5 Duration of follow-up				9.2

Section 4: Source and study populations	Yes	No	N/A	Section Number
4.3 Does the protocol define how the study population will be sampled from the source population? (e.g. event or inclusion/exclusion criteria)				9.2

Comments:

--

Section 5: Exposure definition and measurement	Yes	No	N/A	Section Number
5.1 Does the protocol describe how the study exposure is defined and measured? (e.g. operational details for defining and categorising exposure, measurement of dose and duration of drug exposure)				
5.2 Does the protocol address the validity of the exposure measurement? (e.g. precision, accuracy, use of validation sub-study)				
5.3 Is exposure categorised according to time windows?				
5.4 Is intensity of exposure addressed? (e.g. dose, duration)				
5.5 Is exposure categorised based on biological mechanism of action and taking into account the pharmacokinetics and pharmacodynamics of the drug?				
5.6 Is (are) (an) appropriate comparator(s) identified?				

Comments:

--

Section 6: Outcome definition and measurement	Yes	No	N/A	Section Number
6.1 Does the protocol specify the primary and secondary (if applicable) outcome(s) to be investigated?				9.3.2
6.2 Does the protocol describe how the outcomes are defined and measured?				9.3.2
6.3 Does the protocol address the validity of outcome measurement? (e.g. precision, accuracy, sensitivity, specificity, positive predictive value, use of validation sub-study)				
6.4 Does the protocol describe specific outcomes relevant for Health Technology Assessment? (e.g. HRQoL, QALYs, DALYS, health care services utilisation, burden of disease or treatment, compliance, disease management)				

Comments:

--

Section 7: Bias	Yes	No	N/A	Section Number
7.1 Does the protocol address ways to measure confounding? (e.g. confounding by indication)				
7.2 Does the protocol address selection bias? (e.g. healthy user/adherer bias)				9.9
7.3 Does the protocol address information bias? (e.g. misclassification of exposure and outcomes, time-related bias)				

Comments:

--

Section 8: Effect measure modification	Yes	No	N/A	Section Number
8.1 Does the protocol address effect modifiers? (e.g. collection of data on known effect modifiers, subgroup analyses, anticipated direction of effect)				

Comments:

--

Section 9: Data sources	Yes	No	N/A	Section Number
9.1 Does the protocol describe the data source(s) used in the study for the ascertainment of:				
9.1.1 Exposure? (e.g. pharmacy dispensing, general practice prescribing, claims data, self-report, face-to-face interview)				
9.1.2 Outcomes? (e.g. clinical records, laboratory markers or values, claims data, self-report, patient interview including scales and questionnaires, vital statistics)				9.4
9.1.3 Covariates and other characteristics?				
9.2 Does the protocol describe the information available from the data source(s) on:				
9.2.1 Exposure? (e.g. date of dispensing, drug quantity, dose, number of days of supply prescription, daily dosage, prescriber)				
9.2.2 Outcomes? (e.g. date of occurrence, multiple event, severity measures related to event)				9.4
9.2.3 Covariates and other characteristics? (e.g. age, sex, clinical and drug use history, co-morbidity, co-medications, lifestyle)				
9.3 Is a coding system described for:				
9.3.1 Exposure? (e.g. WHO Drug Dictionary, Anatomical Therapeutic Chemical (ATC) Classification System)				

Section 9: Data sources	Yes	No	N/A	Section Number
9.3.2 Outcomes? (e.g. International Classification of Diseases (ICD), Medical Dictionary for Regulatory Activities (MedDRA))				
9.3.3 Covariates and other characteristics?				
9.4 Is a linkage method between data sources described? (e.g. based on a unique identifier or other)				9.4

Comments:

--

Section 10: Analysis plan	Yes	No	N/A	Section Number
10.1 Are the statistical methods and the reason for their choice described?				9.7.1
10.2 Is study size and/or statistical precision estimated?				9.5
10.3 Are descriptive analyses included?				9.7.1
10.4 Are stratified analyses included?				
10.5 Does the plan describe methods for analytic control of confounding?				
10.6 Does the plan describe methods for analytic control of outcome misclassification?				
10.7 Does the plan describe methods for handling missing data?				
10.8 Are relevant sensitivity analyses described?				9.7.1

Comments:

--

Section 11: Data management and quality control	Yes	No	N/A	Section Number
11.1 Does the protocol provide information on data storage? (e.g. software and IT environment, database maintenance and anti-fraud protection, archiving)				
11.2 Are methods of quality assurance described?				9.10.1
11.3 Is there a system in place for independent review of study results?				

Comments:

--

Section 12: Limitations	Yes	No	N/A	Section Number
12.1 Does the protocol discuss the impact on the study results of: 12.1.1 Selection bias?				9.9

Section 12: Limitations	Yes	No	N/A	Section Number
12.1.2 Information bias?				9.9
12.1.3 Residual/unmeasured confounding? (e.g. anticipated direction and magnitude of such biases, validation sub-study, use of validation and external data, analytical methods).				
12.2 Does the protocol discuss study feasibility? (e.g. study size, anticipated exposure uptake, duration of follow-up in a cohort study, patient recruitment, precision of the estimates)				

Comments:

Section 13: Ethical/data protection issues	Yes	No	N/A	Section Number
13.1 Have requirements of Ethics Committee/ Institutional Review Board been described?				9.10.1
13.2 Has any outcome of an ethical review procedure been addressed?				
13.3 Have data protection requirements been described?				10.2

Comments:

Section 14: Amendments and deviations	Yes	No	N/A	Section Number
14.1 Does the protocol include a section to document amendments and deviations?				5

Comments:

Section 15: Plans for communication of study results	Yes	No	N/A	Section Number
15.1 Are plans described for communicating study results (e.g. to regulatory authorities)?				12
15.2 Are plans described for disseminating study results externally, including publication?				12

Comments:

1. LIST OF ABBREVIATIONS

| | |
|--------|--|
| ACEI | Angiotensin-converting enzyme inhibitors |
| ARB | Angiotensin Receptor Blocker |
| BI | Boehringer Ingelheim |
| CCB | Calcium Channel Blockers |
| CHD | Coronary heart disease |
| CKD | Chronic kidney disease |
| CVD | Cardiovascular disease |
| DMRP | Data management and review plan |
| eGFR | Estimated glomerular filtration rate |
| EMR | Electronic medical records |
| ENCEPP | European Network of Centers for Pharmacoepidemiology and Pharmacovigilance |
| ESRD | End stage renal disease |
| GPP | Good Pharmacoepidemiology Practice |
| HDL | High-density lipoprotein |
| ICD | International classification of disease |
| IDF | International Diabetes Federation |
| IEC | Independent Ethics Committee |
| IRB | Institutional Review Board |
| LDL | Low-density lipoprotein |
| LOS | Length of stay |
| MALB | Microalbumin |
| MI | Myocardial infarction |
| NIS | Non-interventional Study |
| OHA | Oral hypoglycemic agent |
| PI | Principal Investigator |
| SEAP | Statistical and epidemiological analysis plan |
| SOP | Standard Operating Procedures |
| TC | Total cholesterol |
| TG | Triglyceride |

3. PURPOSE AND SCOPE

The research question and objectives, study design, data source, study size, data analysis will be clarified as in the NIS protocol; detailed primary outcomes, secondary outcomes and further outcomes will be shown as tables; software applied in this study will be described for each procedure; Rules handling outliers, inconsistencies and missing values are described in SEAP.

4. AMENDMENTS AND UPDATES

None

5. RESEARCH QUESTION AND OBJECTIVE

The study aimed to investigate the clinical characteristics, treatment, and economic burden of disease of Chinese diabetic/non-diabetic patients with/without established cardiovascular disease, chronic kidney disease, or at high cardiovascular risk, including:

- Primary objectives: describe the proportion of Chinese diabetic/non-diabetic patients with established cardiovascular disease, CKD, or at high cardiovascular risk including hypertension and hyperlipidemia;
- Secondary objectives: describe the demographic characteristics of the last visit for all patients, and the demographic characteristics of inpatients over time; investigate the clinical characteristic for all patients;
- Further objectives: examine economic burden of disease of Chinese diabetic/non-diabetic patients with/without established cardiovascular disease, CKD, or at high cardiovascular risk; explore the trends of clinical characteristics, treatment pattern, economic burden of inpatients over time.

6. RESEARCH METHODS

6.1 STUDY DESIGN

This study is an observational, cross-sectional study based on a routinely collected database. We constructed four groups for comparison: the group A and group B included all diabetic patients with/without established CV disease, CKD, or at high CV risk, respectively. The group C included all non-diabetic patients with established cardiovascular disease, chronic kidney disease, or at high cardiovascular risk. The group D will be constructed to match group A, non-diabetic patients will be included without established cardiovascular disease, chronic kidney disease, and not at high cardiovascular risk. For group D, we will randomly sample study populations to acquire a 1:1 sample of non-diabetic patients without disease by matching on age and gender with group A.

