7.3 Covariates

No applicable. This is a cross-sectional study aiming to describe the proportion, clinical characteristics and economic burden.

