10. DATA ANALYSIS

10.1 Main analysis

The analyses will mainly describe the patient demographic characteristics, comorbidities, complications, treatment pattern and economic burden based on 40 hospitals EMRs of Tianjin regional database.

Characteristics presented as continuous data will be summarized through means, standard deviations, medians, minimum and maximum values; whereas, categorical data will be summarized as counts and proportions.

All tests of statistical significance among different subgroups (age, gender, department, underlying diseases, etc.) will be two-sided unless otherwise specified; any test resulting in $p < 0.05$ will be considered statistically significant. Student-t test, analysis of variance, chi-square test and other rank test will be mainly applied for this study.

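### Age and gender are balanced only between Groups A and D, so the diabetic/non-diabetic comparisons at fixed disease status (A-C and B-D) can carry uncorrected age differences

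*SAP*

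**What the plan says.** SAP 6.1 introduces the groups with "We constructed four groups for comparison". It defines them as a two-by-two of diabetes by disease or risk:

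- **A and B:** "the group A and group B included all diabetic patients with/without established CV disease, CKD, or at high CV risk, respectively".
- **C:** Protocol 9.3.1 states "The group C included all non-diabetic patients with established cardiovascular disease, chronic kidney disease, or at high cardiovascular risk", and SAP 6.1 agrees.
- **D:** non-diabetic and free of the listed conditions. This is the only matched group. Under SAP 6.1 it is sampled to "acquire a 1:1 sample of non-diabetic patients without disease by matching on age and gender with group A", and Protocol 9.3.1 gives the same rule.

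No section matches C to A or D to B. Covariates are declared not applicable in Protocol 9.3.3 and in SAP 7.3, where the reason given is "This is a cross-sectional study aiming to describe the proportion, clinical characteristics and economic burden". The ENCePP checklist (Protocol Annex 2) answers No to stratified analyses (10.4) and No to analytic control of confounding (10.5).

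SAP 7.2.2, Tables 2 to 4, sets Groups A to D side by side by setting and year for age, gender, insurance, discharge department, death, HbA1c, glucose and creatinine. SAP 10.1 adds significance tests: "All tests of statistical significance among different subgroups (age, gender, department, underlying diseases, etc.) will be two-sided unless otherwise specified". It names t-tests, analysis of variance, chi-square and rank tests, with p < 0.05 as the criterion.

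**The concern.** The rationale in Protocol 7 raises the possibility that characteristics and treatment differ between patients with and without diabetes. Two pairs of groups bear on that with disease/risk status held constant: A against C, and B against D. Neither is balanced on age or gender. The pair that is balanced, A-D, changes both factors, so a difference there cannot be assigned to either one.

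The matching also affects B-D. Drawing D to fit A gives D the ages of diabetic patients who have disease or risk. B consists of diabetic patients with no recorded cardiovascular disease, heart failure, CKD, hypertension or hyperlipidaemia, and keeps its own age distribution. Outcomes such as death, creatinine and insurance type can be expected to vary with age. An age difference in B-D or A-C could therefore appear in Tables 3 and 4, with a small p-value, and be read as a difference between diabetic and non-diabetic patients.

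**Working it through.** The documents contain no power, precision or event calculation for these comparisons, so there is no figure of the plan's own to reproduce. The check has three steps.

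**1. What each comparison changes**

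| Comparison | Diabetes differs | Disease/risk label differs | Age and gender balanced by design |
|---|---|---|---|
| A-D | yes | yes | yes, overall |
| A-C | yes | no | no |
| B-D | yes | no | no |
| A-B | no | yes | no |
| C-D | no | yes | no |

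The only balanced row is the one in which both factors change. This step needs no assumption.

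**2. How the matching enters B-D**

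If every Group A patient receives a close match, mean age(D) = mean age(A). Then mean age(B) − mean age(D) = mean age(B) − mean age(A), and whatever age gap separates A from B also separates D from B.

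**3. Size on assumed figures**

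*Death.* Assume no diabetes effect, a death risk that multiplies by f per 10 years of age, and B younger than D by g years. The B-D ratio is f^(−g/10).

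- f = 2: 2^(−0.5) = 0.71 at 5 years, 2^(−1) = 0.50 at 10 years, 2^(−1.5) = 0.35 at 15 years.
- At 10 years: f = 1.5 gives 0.67 and f = 2.5 gives 0.40.

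*A continuous outcome tested by t-test.* Assume no diabetes effect and an outcome that rises b SD per year of age. The spurious difference is d = g × b. With SE = √(1/nB + 1/nD), the chance of p < 0.05 in the direction of the age gap is Φ(d/SE − 1.96). With no gap it would be 0.025.

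Inputs: diabetic patients with comprehensive data number 100,000 in Protocol 9.4 and 10,000 in SAP 8. The two conflict, so both are used as a range. By the 1:1 rule nD = nA. Assumed: A is 70% to 90% of diabetic patients, and b is 0.01 to 0.03.

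Worked example with A at 90%, g = 5 and b = 0.01, so d = 0.05:

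- SAP total: nB = 1,000, nD = 9,000, SE = 0.0333, d/SE = 1.50, Φ(−0.46) = 0.32.
- Protocol total: nB = 10,000, nD = 90,000, SE = 0.0105, d/SE = 4.74, Φ(2.78) = 0.997.

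Ranges over the assumed shares and slopes:

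| B-D age gap | 10,000 diabetic patients | 100,000 diabetic patients |
|---|---|---|
| 2 years | 0.09 to 0.79 | 0.48 to 1.00 |
| 5 years | 0.32 to 1.00 | 0.997 to 1.00 |
| 10 years | 0.85 to 1.00 | 1.00 |

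For A-C with a 5-year gap, A at 80% of diabetic patients, C at 0.5 to 2 times A and b of 0.01 to 0.02, the chance is 0.73 to 1.00 when A = 8,000 and 1.00 when A = 80,000. These figures use whole groups. Splitting by setting and year, as Tables 2 to 4 do, gives smaller cells and lower chances.

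*Effect of age control.* A simulation had 200,000 patients per group, b = 0.02 and no diabetes effect. The crude B-D differences were −0.04, −0.10 and −0.20 SD for gaps of 2, 5 and 10 years. With age in the model, all three were within 0.005 SD of zero.

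**The case against.** The strongest reply is that the study is descriptive. Its objectives are to describe, investigate, examine and explore. The ENCePP checklist marks hypotheses, measures of association and comparators as not applicable. No section names A-C, B-D or A-D as a contrast, and crude values for each group as it presents are a legitimate target. This stands to the extent that the plan states no diabetes estimand and so cannot be said to have failed one. It does not dispose of the point, because SAP 6.1 builds the groups to be compared and SAP 10.1 attaches p-values. The test wording in SAP 10.1 does not clearly schedule A-C or B-D tests, but underlying diseases are among the subgroups it lists.

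Second, Table 2 reports age and gender by group, setting and year, so a reader would see an imbalance. That is true, but seeing the gap does not remove it from death or creatinine in Tables 3 and 4.

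Third, every figure for size is assumed. That stands in full.

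Fourth, analysis text for the further outcomes is not in the public documents, so how length of stay and cost are compared cannot be judged. The checklist's No on confounding control makes hidden adjustment unlikely, but this point is confined to the outcomes in Tables 3 and 4 and insurance type.

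A reader might infer three stronger things that the documents do not support:

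- That A-C and B-D would isolate diabetes once age and gender were controlled. The mix of cardiovascular disease, CKD, hypertension and hyperlipidaemia can still differ between A and C, and other differences between tertiary-hospital patients remain.
- That diabetes will look protective among disease-free patients. This needs B to be younger than A, which is plausible but not documented.
- That matching D to A makes B-D worse than an unmatched D would. This depends on the ages of the unmatched pool, which are not given.

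**Conclusion.** The point holds as a gap in design and analysis. Age and gender are balanced only for the pair that differs in both diabetes and disease/risk. The pairs that hold disease/risk status constant have no control by design or analysis, and the matching carries any A-B age gap into B-D. That last statement assumes that nearly all of Group A is matched closely on age.

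The effect on results is unknown in size and direction, because no group ages are given. The death ratios and rejection probabilities show only that, at this study's scale, age gaps of a few years could produce significant differences with no diabetes effect. Matching a disease-free reference group to A is a defensible choice and can stay. This is an inexpensive improvement in how the groups are compared and labelled. It does not invalidate the descriptive aims.

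**What to change.** Keep matched Group D and all crude columns, and make these changes:

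- **SAP 7.2.2:** for the outcomes in Tables 3 and 4 and for insurance type, add values for B and C directly standardised to Group A's age-by-gender distribution, for example in 5-year bands by sex. Standardise D as well within setting and year cells, where overall matching need not hold. State the standard explicitly; using Group A in the same cell means A's crude value needs no weighting. A second, unmatched Group D is not needed, since matched D already has A's distribution overall.
- **SAP 10.1:** base any A-C or B-D test on the standardised or age- and gender-adjusted comparison.
- **SAP 6.1:** state that A-D is a joint contrast of diabetes and disease/risk, and that standardised A-C and B-D remain descriptive and do not isolate diabetes.
- **Table 2:** mark Group D's age and gender rows as matching variables, not findings.

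Birthday and sex are already collected (Protocol 9.3, Table 1), so no new data are required. The cost is SAP wording, extra columns across settings and three years, and merging of some sparse age bands.
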